[figure not shown]

**NON-INTERVENTIONAL STUDY OF ADVANCED RENAL CELL CARCINOMA
TREATMENT PATTERNS AND UNMET NEEDS**

This document contains confidential information belonging to Pfizer. Except as otherwise agreed to in writing, by accepting or reviewing this document, you agree to hold this information in confidence and not copy or disclose it to others (except where required by applicable law) or use it for unauthorized purposes. In the event of any actual or suspected breach of this obligation, Pfizer must be promptly notified.

PFIZER CONFIDENTIAL

Title	Study of advanced renal cell carcinoma treatment patterns and unmet needs using real world claims and electronic medical record data.
Protocol number	A6181232
Protocol version identifier	01
Date of last version of protocol	4 October 2019
Research question and objectives	
The study aims to assess treatment patterns and outcomes in advanced RCC patients in real world clinical practices across various real world databases. Four databases will be evaluated: IBM's Truven MarketScan Commercial, Optum Clininformatics, the IMS PharMetrics claims databases and The PanTher (which has both Humedica EMR data including EMR notes linked to Optum claims).
 
The primary study objectives include:
 
Treatment patterns: Characterize first-line and subsequent lines of therapy. Treatment patterns will be summarized for the following therapy regimens:
• immuno-oncology (IO) monotherapy;• IO+IO combo-therapy;• IO+tyrosine kinase inhibitor (TKI) combo-therapy;• TKI monotherapy;• Other.Analyze Cohorts of Interest: To describe patient demographics and clinical characteristics, and select outcomes of interest among the following first-line advanced RCC cohorts of interest:
• immuno-oncology (IO) monotherapy;• IO+IO combo-therapy;• IO+tyrosine kinase inhibitor (TKI) combo-therapy;• TKI monotherapy;• Other.

PFIZER CONFIDENTIAL

	
3. Analyze Select Outcomes of Interest:
 
• Time to Treatment Failure (TTF) - the time from therapy start to treatment discontinuation or therapy change (next line of therapy – switch or augment), end of enrollment, or death;• Treatment Interruption – those with gaps in treatment greater than allowable gap but who restart the same medication with no indication of switching or augmentation;• Health Care Costs (inpatient, outpatient, pharmacy, other);• Health Care Utilization (inpatient hospitalizations, ER, outpatient visits);• Survival Time and Landmark Survival. Mean/median survival time and % of population surviving 3, 6, and 12 months will be explored, although regimens are too new for extensive follow-up time. (Note: survival analysis will only be available in the Optum Clininformatics Database).
	
PPD [REDACTED], PharmD, MSc Director, PPD [REDACTED] [REDACTED] New York, NY 10017 Email: PPD [REDACTED]
 
PPD [REDACTED] Sr. Director, PPD [REDACTED] [REDACTED] Rockland, MA 02370 Email: PPD [REDACTED]
 
PPD [REDACTED], MD Title Address Email: PPD [REDACTED]
 
PPD [REDACTED] Executive Director, PPD [REDACTED] [REDACTED] New York, NY 10017 Email: PPD [REDACTED]

PFIZER CONFIDENTIAL

[REDACTED]

	PPD [REDACTED], MPH Director, PPD [REDACTED] New York, NY 10017 Email: PPD [REDACTED]
	PPD [REDACTED], MPH Manager, PPD [REDACTED] New York, NY 10017 Email: PPD [REDACTED]
	PPD [REDACTED] Intern, PPD PPD New York, NY 10017 Email: PPD [REDACTED]

PFIZER CONFIDENTIAL

[REDACTED]

TABLE OF CONTENTS

[figure not shown]
[figure not shown]
1. LIST OF ABBREVIATIONS.....	7
2. RESPONSIBLE PARTIES.....	9
3. AMENDMENTS AND UPDATES.....	10
4. RATIONALE AND BACKGROUND.....	10
5. RESEARCH QUESTION AND OBJECTIVES	11
6. RESEARCH METHODS	12
6.1. Study Design	12
6.2. Setting.....	17
6.2.1. Inclusion Criteria	17
6.2.2. Exclusion Criteria	18
6.3. Variables.....	19
6.3.1. Treatment Pattern Variables	19
6.3.2. Baseline Variables	21
6.3.3. Outcomes Variables.....	26
6.3.4. Cost and Utilization Variables.....	27
6.4. Data Sources.....	30
6.5. Study Size.....	33
6.6. Data Management	33
6.6.1. Record Retention	33
6.7. Data Analysis	34
6.8. Quality Control.....	35
6.9. Limitations of the Research Methods.....	35
6.10. Other Aspects	35
7. PROTECTION OF HUMAN SUBJECTS	35
7.1. Patient Information.....	35
7.2. Patient Consent.....	35
7.3. Institutional Review Board (IRB)/Independent Ethics Committee (IEC)	35

1. LIST OF ABBREVIATIONS

Table 1. Abbreviations

Abbreviation	Definition
AE	adverse event
AGI	Analysis Group, Inc.
aRCC	Advanced Renal Cell Carcinoma
CIOMS	Council for International Organizations of Medical Sciences
CI	confidence interval
EMA	European Medicines Agency
ENCePP	European Network of Centres for Pharmacoepidemiology and Pharmacovigilance
FDA	Food and Drug Administration
GEP	Good Epidemiological Practice
GPP	Guidelines for Good Pharmacoepidemiology Practices
Hb	hemoglobin
HR	hazard ratio
IRB	Institutional Review Board
IEA	International Epidemiological Association
IEC	Independent Ethics Committee
IMDC	International Metastatic Renal Cell Carcinoma Database Consortium
IO	Immuno-oncology
ISPE	International Society for Pharmacoepidemiology

PFIZER CONFIDENTIAL

Abbreviation	Definition
ISPOR	International Society for Pharmacoeconomics and Outcomes Research
LDH	lactate dehydrogenase
LLN	Lower limit of normal
LSLV	last subject last visit
mRCC	Metastatic Renal Cell Carcinoma
NCCN	National Comprehensive Cancer Network
OS	overall survival
PPPM	Per Patient Per Month
PFS	progression free survival
RCC	Renal cell carcinoma
SAP	Statistical Analysis Plan
SD	standard deviation
TKI	Tyrosine kinase inhibitor
TTD	time to treatment discontinuation

PFIZER CONFIDENTIAL

3. AMENDMENTS AND UPDATES

Table 3. Amendments and Updates

Amendment number	Date	Protocol section(s) changed	Summary of amendment(s)	Reason

[figure not shown]
4. RATIONALE AND BACKGROUND

Approximately 2% of all incident malignant tumors worldwide are caused by renal cancers.¹ In 2019, The American Cancer Society for Kidney Cancer in the United States estimates that there will be about 73,820 cases of kidney cancer. It also estimates that about 14,770 people will die from this disease.² RCC often gets diagnosed in advanced stages: ~25-30% of the patients are diagnosed at the metastatic disease stage.³ Hence, patients with advanced disease often have high rates of morbidity and mortality.⁴ Until 2005, cytokine therapy was the only approved post-surgical treatment of advanced RCC. These therapies were highly toxic and offered limited long-term clinical benefit in a majority of patients. This was followed by targeted therapies for treatment of mRCC with sorafenib in December 2005 and sunitinib in January 2006.⁵ The US Food and Drug Administration (FDA)-approved tyrosine kinase inhibitors (TKIs) have expanded to included axitinib (January 2012) and pazopanib (October 2009).⁶ The 5-year relative survival rates for these therapies have ranged from 10.4% for patients with later-stage disease involving distant metastases to 90.4% for early-stage localized disease.⁷

Treatment guidelines are determined by prognostic risk group using the International Metastatic Renal Cell Carcinoma Database Consortium (IMDC) Criteria⁸ or Memorial Sloan Kettering Cancer Center Prognostic Model (MSKCC).⁹ According to 2019 NCCN guidelines, targeted therapy utilizing tyrosine kinase inhibitors, TKIs and/or VEGF antibodies (including pazopanib, sunitinib, bevacizumab, , axitinib, and cabozantinib) are recommended as first-and second-line treatments. Mammalian target of rapamycin (mTOR) (temsirolimus and everolimus) are also used in this setting. Immune checkpoint inhibitors, which alter the interaction between immune cells and antigen-presenting cells, are the new revolution in treatment options.¹⁰

In April 2018, the FDA approved the combination of the immuno-oncology (IO) checkpoint inhibitors ipilimumab and nivolumab for advanced RCC.¹¹ This combination is currently recommended as the new standard of care for first-line for treatment of metastatic RCC (mRCC) patients with intermediate or poor prognosis.¹²

PFIZER CONFIDENTIAL

This study will clarify current treatment patterns and unmet needs (eg, regimen adherence and discontinuation patterns) among the various regimens used to treat mRCC. This study characterize mRCC treated populations represented by the most prevalent treatment regimens and will quantify mRCC outcomes including treatment failure/duration of therapy, cost and utilization and survival in real world clinical practices toward demonstrating current unmet needs in mRCC.

5. RESEARCH QUESTION AND OBJECTIVES

The study aims to address the following key objectives among patient cohorts diagnosed with advanced/metastatic RCC:

Objective 1: Treatment patterns: Characterize first-line and subsequents lines of therapy. Treatment patterns will be summarized for the following therapy regimens:

- immuno-oncology (IO) monotherapy;
- IO+IO combo-therapy;
- IO+tyrosine kinase inhibitor (TKI) combo-therapy;
- TKI monotherapy;
- Other.

Objective 2: Analyze Cohorts of Interest: To describe patient demographics and clinical characteristics, and select outcomes of interest among the following first-line advanced RCC cohorts of interest:

- immuno-oncology (IO) monotherapy;
- IO+IO combo-therapy;
- IO+tyrosine kinase inhibitor (TKI) combo-therapy;
- TKI monotherapy;
- Other.

Objective 3: Analyze Select Outcomes of Interest:

- **Time to Treatment Failure (TTF)** - the time from therapy start to treatment discontinuation or therapy change (next line of therapy – switch or augment), end of enrollment, or death.

PFIZER CONFIDENTIAL

- **Treatment Interruption** – those with gaps in treatment greater than allowable gap but who restart the same medication with no indication of switching or augmentation.
- **Health Care Costs** (inpatient, outpatient, pharmacy, other).
- **Health Care Utilization** (inpatient hospitalizations, ER, outpatient visits).
- **Survival Time and Landmark Survival.** Mean/median survival time and % of population surviving 3, 6, and 12 months will be explored, although regimens are too new for extensive follow-up time. (Note: survival analysis will only be available in the Optum Clininformatics Database).

6. RESEARCH METHODS

This master protocol specifies more than one retrospective, longitudinal cohort studies that will be performed and replicated in various de-identified, real world administrative medical and pharmacy claims data and electronic medical records structured data. Leveraging multiple databases will optimize the study sample size and provide more robust foundation to addressing the research questions. The analyses will be performed using real world claims and EMR data, including Optum Clininformatics Claims, Truven Marketscan Commercial Claims, Pharmetrics Claims and the Optum PanTHER containing the overlap of Optum claims and Humedica EMR structured data. It should be noted that contractual obligations associated with these datasources require that they not be merged or combined.

6.1. Study Design

Patients receiving aRCC treatment (see [Table 4](#)), between April 2018 and the present, who have no prior aRCC treatment in their claims history will be identified for this study. The index date for each analysis will be defined as the date of initiation of the aRCC treatment. Patients must have at least 2 RCC diagnoses at least 30 days apart to be included. Patients must also have 2 secondary malignancy ICD9 or ICD10 codes (often used in claims data to suggest cancer metastases) at least 30 days apart in the 12 months pre and one month post index aRCC treatment. [CCI](#)

Various algorithms and temporal relationships between the secondary malignancy codes, RCC diagnosis codes and other cancer codes were explored toward developing the criteria for metastatic advanced RCC for this study.

Study will require a minimum of 12 months of enrollment prior to the index date. Feasibility was assessed for various lengths of continuous enrollment criteria (3, 6 and 12 months post index date) toward understanding sample sizes available for analysis and follow-up periods. Study outcomes will be assessed for three patient cohorts (3, 6 and 12 month cohorts) according to their available months of continuous enrollment.

PFIZER CONFIDENTIAL

First line therapy cohorts will first be presented for all patients regardless of follow-up time available. Baseline characteristics, costs and utilization will be measured over the 6 months prior to the index date. Duration of therapy and utilization analysis will require at least 6 months of post-index enrollment, with sub-analysis preformed on the cohorts with 3-months and 12-months of post-index enrollment. Utilization and cost will be performed per-utilizer-per-month (PUPM), and then separately for each of the cohorts with 3-month, 6-month and 12-months of post-index enrollment.

The analysis will focus on, but is not limited to, the following regimens:

- a. **Combo IO:** nivolumab combined with ipilimumab;
- b. **Monotherapy TKI:** sunitinib, cabozantinib, and pazopanib;
- c. **Combo TKI + IO:** avelumab in combination with axitinib, pembrolizumab in combination with axitinib;
- d. **Other:** all others regimens.

PFIZER CONFIDENTIAL

[figure not shown]
[figure not shown]
[figure not shown]

Figure 1: Cohort Identification

Analysis 1. Treatment Patterns and Duration

The purpose of this initial analysis is to characterize the treatment patterns and treatment duration of adult patients with advanced and metastatic RCC across various real world claims databases (Truven, Optum and Pharmetrics claims). Treatment patterns for these various US population based claims dataset will be assessed for consistency and regimen-specific population differences, as well as assessing feasibility for sub-analyses.

In order to isolate lines of therapy of interest, all medications used for advanced RCC must be considered. Thus, lines of therapy will be performed considering the following RCC medications (see [Table 4](#)):

PFIZER CONFIDENTIAL

Table 4. Medications of Interest

Drug Class	Ingredient	Brand Name	Dosage Form	Mechanism
TKI	Pazopanib	Votrient	Oral	Tyrosine Kinases Inhibitor
TKI	Sunitinib	Sutent	Oral	Multiple receptor tyrosine kinases (RTKs)
TKI	Axitinib	Inlyta	Oral	Kinase inhibitor
TKI	Cabozantinib	Cabometyx/Cometriq	Oral	New Novel TKI
TKI	Sorafenib	Nexavar	Oral	Multikinase inhibitor
TKI	Levantinib	Lenvima	Oral	RTK inhibitor
TKI	Erlotinib	Tarceva	Oral	Epidermal Growth Factor Receptor tyrosine kinase inhibitor
mTOR	Temsirolimus	Torisel	Both oral and IV	Inhibitor of mammalian target of rapamycin
mTOR	Everolimus	Afinitor	Both oral and IV	Mammalian target of rapamycin inhibitor
IO	Ipilimumab	Yervoy	Injection	Human cytotoxic T-lymphocyte antigen 4 (CTLA-4)-blocking antibody
IO	Nivolumab	Opdivo	Injection	Checkpoint monoclonal Antibody PD-1 Inhibitor
IO	Atezolizumab	Tecentriq	Injection	Checkpoint monoclonal Antibody PD-L1 Inhibitor
IO	Durvalumab	Imfinzi	Injection	Checkpoint monoclonal Antibody PD-L1 Inhibitor
IO	Pembrolizumab	Keytruda	Injection	Checkpoint monoclonal Antibody PD-1 Inhibitor
IO	Avelumab	Bavencio	Injection	Checkpoint monoclonal Antibody PD-L1 Inhibitor
IO	Bevacizumab	Avastin	Injection	Recombinant monoclonal antibody VEGF/VEGFR Inhibitor

First-line and subsequent lines (up to 3) of monotherapy and combo-therapy regimens for aRCC patients will be identified and the following metrics will be considered for first-line of therapy:

- Time from first ever metastatic diagnosis to first line regimen;
- Duration of first line therapy;
- Patterns of switching, augmentation and discontinuation;
- Treatment interruptions.

Treated Period Follow-Up. Patients will be followed over the period treated with advanced RCC therapy. Time treated will be defined as the time from the index date to the date of the end of the last advanced metastatic RCC prescription (end of supply for orals/administration date plus 30 days for injectables), end of enrollment, end of follow up, or death (see more specifics on oral versus injectable rules in [6.3.1 Variables](#) section of this protocol).

Analysis 2. Describe various treated populations of interest by demographics, clinical characteristics, as well as cost and utilization

Describe the demographics and other baseline characteristics of the first-line treated cohorts of interest identified in the treatment patterns analysis (Analysis 1) for RCC patient as follows:

Baseline Characteristics (see [6.3.2 Baseline Characteristics](#)):

- Age at index;
- Gender;
- Race;
- Region;

PFIZER CONFIDENTIAL

- Payor;
- Clinical characteristics: Quan-Charlson Comorbidity Index (CCI) scores and baseline comorbidities;
- Prior treatment (6 months prior) - nephrectomy, radiation/ablation, interferon, high-dose interleukin-2, other anti-neoplastic medications;
- Secondary malignancy locations (6 months prior);
- Baseline costs of care (6 months prior);
- Baseline health care resource utilization (6 months prior).

Analysis 3: Evaluate the key outcomes of interest for advanced RCC therapy regimens toward demonstrating existing unmet needs in RCC given currently available therapies (eg, ipilimumab/nivolumab).

Treatment duration, discontinuation, interruption, switching and therapy augmentation will be presented, as will the burden of disease costs and health care utilization. Survival will also be explored, although regimens are too new for extensive follow-up time.

Overall Outcomes Study Period. For the outcomes analysis, follow-up will be defined as the time from the index date to the end of specified follow up period of 6 months, end of enrollment, or death. Follow-up may vary given sample sizes of study population, with by subanalysis using 1-year or 2-years of follow-up time from study index date for certain sub-populations.

Outcomes include:

- **Time to Treatment Failure (TTF)** – First line time to treatment failure (TTF) is defined as the time from first-line therapy start to treatment discontinuation for any reason, including switched, augmented therapy, end of enrollment, death.
- **% continuing** – those with no gap in therapy greater than 30 days and who do not begin a new treatment during the study period.
- **% discontinuing** – those with gap in therapy greater than 30 days and who do not begin a new treatment.
- **% with treatment interruption** - those with gap in therapy greater than 30 days but who eventually continue the original treatment (have an additional administration or refill) and do not switch or augment therapy during the study period.
- **% switching** – those with gap in therapy greater than 30 days and who begin a new treatment.
- **% augmenting** – those who begin a new treatment but continue using the original treatment (have an additional administration or refill) and do not have a gap in therapy greater than 30 days of their original treatment.
- **Overall and aRCC Follow-Up Costs:** Total and RCC-specific pharmacy, medical costs from aRCC therapy index through follow-up period (costs summarized as: mean, median costs per patient and costs per patient per month).

PFIZER CONFIDENTIAL

- **Overall and aRCC Follow-Up Utilization:** Total and RCC-specific inpatient, ER, outpatient visits from aRCC therapy index through follow-up period (utilization will be summarized as: mean, median utilization per patient and utilization per patient per month).
- **Overall landmark survival:** Using Optum claims and PanTher data, landmark survival will be described and compared over follow-up time periods (3, 6, 12 months).
- **Mean/Median Survival:** Using Optum claims and PanTher data median survival time will be described and compared over follow-up time periods determined after feasibility assessments of cohorts of interest.

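### Section 6.1 has no IO monotherapy group, although the synopsis and Objectives 1 and 2 require one, and its catch-all sends those patients to Other

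*Combined protocol and SAP*

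**What the plan says.** Section 5, matching the synopsis, lists the same five groups under Objectives 1 and 2: "immuno-oncology (IO) monotherapy", IO+IO, "IO+tyrosine kinase inhibitor (TKI) combo-therapy", "TKI monotherapy" and Other. No drug is named in any of them. Objective 2 makes these groups the basis for describing patients and "select outcomes of interest among the following first-line advanced RCC cohorts of interest".

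Section 6.1 introduces its list with "The analysis will focus on, but is not limited to, the following regimens" and gives four items:

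- a, Combo IO: "nivolumab combined with ipilimumab"
- b, Monotherapy TKI: "sunitinib, cabozantinib, and pazopanib"
- c, Combo TKI + IO: avelumab with axitinib, and pembrolizumab with axitinib
- d, Other: "all others regimens"

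Table 4 lists the agents used to build lines of therapy: 7 TKIs, 2 mTOR inhibitors and 7 agents classed as IO. The last group includes bevacizumab, whose listed mechanism is VEGF/VEGFR inhibition.

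Analysis 2 takes its cohorts from Analysis 1, and Analysis 1 restates no regimen list. Section 6.7 says that no separate SAP is required. Section 6.8 says that programming follows the protocol.

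**The concern.** The objectives and the design section group patients differently, and the visible text does not say which grouping applies. IO monotherapy is a named cohort in one place and part of the residual group in the other. An analyst who follows Section 6.1 would produce no IO monotherapy column, and Other would mix single-agent IO with mTOR drugs and any regimen not listed.

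Cohort assignment carries through to most of the output. Section 6.3.4 reports costs and utilization for each regimen-based cohort within each line of therapy. The study is also to be replicated in four databases that may not be merged, and Analysis 1 checks treatment patterns across the claims databases for consistency. If the cohorts were built from Section 5 in one database and from Section 6.1 in another, a difference in definition could look like a difference between databases.

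**Working it through.** The plan states no figure on this point, so there is nothing to reproduce. The check classifies every single agent and every two-drug pair from Table 4 twice: by the Section 5 classes, and by a literal reading of Section 6.1 in which only the regimens named in a to c leave Other.

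**Inputs.** From Table 4: TKI = 7, IO = 7 (6 if bevacizumab is not counted as IO). Named in Section 6.1: 0 IO single agents, 3 TKI single agents, 2 IO+TKI pairs, 1 IO+IO pair. None of the named regimens contains bevacizumab.

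**Formulas.** Single agents = number in class. IO+TKI pairs = IO × TKI. IO+IO pairs = IO × (IO − 1) / 2. Moved to Other = possible − named.

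| Section 5 group | Item in 6.1 | Possible | Named in 6.1 | Moved to Other | Moved, bevacizumab not IO |
|---|---|---|---|---|---|
| IO monotherapy | none | 7 | 0 | 7 of 7 | 6 of 6 |
| TKI monotherapy | b | 7 | 3 | 4 of 7 | 4 of 7 |
| IO+TKI | c | 7 × 7 = 49 | 2 | 47 of 49 | 6 × 7 = 42, so 40 of 42 |
| IO+IO | a | 7 × 6 / 2 = 21 | 1 | 20 of 21 | 6 × 5 / 2 = 15, so 14 of 15 |

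The four TKIs not named for monotherapy are axitinib, sorafenib, lenvatinib (spelled Levantinib in Table 4) and erlotinib. Axitinib appears in both named IO+TKI pairs, and Section 4 includes it among the agents recommended in first and second line, but Section 6.1 does not list it as monotherapy.

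These are counts of possible regimens, not patients, and most of the pairs may never occur in the data.

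The rows differ in strength. In the first row the whole group is missing, so no reading of the drug names in a to c restores it. The other three rows depend on whether the named drugs define the groups or illustrate them.

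**The case against.** The strongest reply is that Section 6.1 is a focus list and does not define cohorts. Its opening words say that it is not exhaustive, and that qualifier would be idle if a to d were a strict partition. On that reading the named drugs are examples, axitinib and the other unlisted TKIs remain in the TKI class, and all five cohorts can be built from Section 5 and the class column of Table 4. Drug-level records are kept either way, so regrouping would recover the IO monotherapy cohort. Figure 1 (cohort identification) is not shown and part of the combination-therapy definition in Table 5 is redacted; either could bear on assignment. The programming plan mentioned in Section 6.8 could also settle it, but it is not part of the documents.

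Much of this stands for TKI monotherapy, IO+TKI and IO+IO, which is why those parts are stated conditionally. It does not dispose of IO monotherapy. A non-exhaustive opening might allow further groups, but item d already takes every remaining regimen, and the list never says that IO monotherapy is separate from it.

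A reader might infer three stronger points that the documents do not support:

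- That the objectives require individual TKI regimens as cohorts. They require one class-level TKI monotherapy cohort and one class-level IO+TKI cohort.
- That Objective 2 cannot be answered. Only its IO monotherapy part is lost, and only if Section 6.1 governs; the other cohorts might change in composition.
- That Other has different meanings in different planned tables. Table 8 refers only to regimen-based cohorts, and no table is shown using the Section 6.1 grouping.

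**Conclusion.** The point holds in two parts. Without condition, Section 6.1 lists four groups against five in Section 5, and the missing one is IO monotherapy; read literally, all single-agent IO patients go to Other. Conditionally, if the drugs named in items a to c are definitions, TKI monotherapy covers 3 of 7 Table 4 TKIs, IO+TKI two pairs and IO+IO one pair.

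The effect in patients cannot be computed, because the documents give no counts by regimen. The study is descriptive, so the effect is on cohort composition and on what the tables mean; no error rate or sample size is involved. The conclusion rests on the visible text, with Figure 1 and the redacted part of Table 5 unseen. The sections should be reconciled before cohorts are programmed, since a cohort named in the objectives is at stake and the change is small.

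**What to change.** Replace the list in Section 6.1 with the five Section 5 cohorts: IO monotherapy, IO+IO, IO+TKI, TKI monotherapy and Other. State that the regimens now named in items a to c are sub-rows within these class cohorts and do not limit them. Map every Table 4 agent to exactly one class, and point Analyses 1 to 3 to that mapping.

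Place bevacizumab explicitly. A rule based on the Table 4 class makes it IO, while a rule based on checkpoint inhibition does not, so the text cannot use the two interchangeably. Either recode it as non-IO in Table 4, in which case its regimens go to Other, or state that the IO label is intended.

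The cost is wording in Section 6.1 and Table 4, plus the cohort code. No additional data are needed.

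### Table 4 classes bevacizumab as IO against its own mechanism entry and Section 4, while the Section 6.1 regimen list read literally puts it in Other, so one regimen has two possible cohorts

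*Combined protocol and SAP*

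**What the plan says.** Table 4 in Section 6.1 lists 16 medications with a drug class and a mechanism for each. Seven carry the class IO. Six of these are described as CTLA-4, PD-1 or PD-L1 agents. The seventh, bevacizumab, is described as a "Recombinant monoclonal antibody VEGF/VEGFR Inhibitor".

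Section 4 treats the drug differently. It names bevacizumab under targeted therapy, among "TKIs and/or VEGF antibodies (including pazopanib, sunitinib, bevacizumab, , axitinib, and cabozantinib", and then introduces another class: "Immune checkpoint inhibitors, which alter the interaction between immune cells and antigen-presenting cells, are the new revolution in treatment options". Where Section 4 uses the abbreviation IO, it refers to "the combination of the immuno-oncology (IO) checkpoint inhibitors ipilimumab and nivolumab".

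The front summary and Section 5 both set out to describe "select outcomes of interest among the following first-line advanced RCC cohorts of interest". The cohorts are named by class, starting with "immuno-oncology (IO) monotherapy", followed by IO+IO, IO+TKI, TKI monotherapy and Other.

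Section 6.1 also has a list by drug name, introduced by "The analysis will focus on, but is not limited to, the following regimens". Combination IO there is nivolumab with ipilimumab. Combination TKI and IO is axitinib with avelumab or with pembrolizumab. Monotherapy TKI is sunitinib, cabozantinib or pazopanib. Item d takes every remaining regimen as Other. No bevacizumab regimen is named.

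**The concern.** Table 4 contradicts itself within one row, and it contradicts Section 4. This would be cosmetic if the class column served no purpose. However, the cohorts are named by class, and no other table or text shown says for every drug which class it belongs to. A programmer who needs to know which drugs are IO would naturally look there.

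Bevacizumab can reach the cohorts. Section 6.1 points to Table 4 for the treatments that identify patients, Section 6.2.1 sets the index date at the first advanced RCC medication, and Table 5 builds combinations from any second medication within 30 days. Table 9 gives bevacizumab an imputed days supply for the treatment-pattern and duration work. No visible text sets a special rule for it.

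What is at stake is the content of the IO cohorts. Patients on bevacizumab alone or with a TKI would be described as IO recipients although they had no checkpoint inhibitor. Patients on bevacizumab with one checkpoint inhibitor would be pooled with patients on two. Baseline characteristics, treatment patterns, costs, utilization and outcomes are all summarised by these cohorts.

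**Working it through.** The plan states no figure that depends on this point, so there is nothing to reproduce. The check is a comparison of the two rules, then a count of the regimen definitions affected.

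**The two rules side by side**

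| Regimen | Built from Table 4 classes | Section 6.1 list, read literally |
|---|---|---|
| Bevacizumab alone | IO monotherapy | Other |
| Bevacizumab + a TKI | IO+TKI | Other |
| Bevacizumab + one checkpoint inhibitor | IO+IO | Other |
| Bevacizumab + an mTOR drug | Other | Other |

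The two rules disagree in the first three rows.

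**Count of definitions**

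Inputs from Table 4: 7 TKI, 2 mTOR and 7 IO (6 checkpoint agents plus bevacizumab), so 7 + 2 + 7 = 16 drugs. Only regimens of one or two drugs are counted.

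- Regimens containing bevacizumab: 1 alone + 15 pairs = 16.
- Labelled IO through Table 4: 1 (IO monotherapy) + 7 (IO+TKI) + 6 (IO+IO) = 14 of 16. The 2 mTOR pairs are Other either way.
- Of these 14, with no checkpoint inhibitor: 1 + 7 = 8. The other 6 contain one.

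Possible regimens in each cohort:

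| Cohort | Table 4 as written | Bevacizumab not IO |
|---|---|---|
| IO monotherapy | 7 | 6 |
| IO+IO | C(7,2) = 21 | C(6,2) = 15 |
| IO+TKI | 7 × 7 = 49 | 6 × 7 = 42 |

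These figures count theoretical definitions with equal weight. They say nothing about how often each regimen occurs.

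**Effect on a cohort summary**

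If k of n patients in a cohort are bevacizumab patients, the cohort mean differs from the mean of the other n − k patients by (k/n) × (difference in means between the two groups). The documents give neither k, n nor the difference. As an assumption only, k = 0, 1 or 3 gives shares of 0%, 3.3% or 10% for n = 30, and 0%, 0.7% or 2% for n = 150. These values illustrate scale and are not evidence of impact.

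Each patient's own line dates, gaps and time to treatment failure do not depend on the class label. Only the cohort in which they are summarised does.

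**The case against.** The strongest reply is that Table 4 has a different job. Section 6.1 introduces it as the list of drugs to consider when lines of therapy are isolated, and no visible sentence makes its class column the cohort rule. This stands. A reader might infer that the plan assigns cohorts from that column and that the IO results will therefore be wrong. The documents do not support that; the consequence is conditional.

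The second reply is that the drug-name list in Section 6.1 already sends every bevacizumab regimen to Other. Read literally, it does, and this weakens the concern. It does not settle it: the list is expressly not limited to its items and has no IO monotherapy entry, so it cannot by itself define the five Section 5 cohorts. What remains is two readings with different answers.

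Third, Figure 1, on cohort identification, is not shown, and text after the combination definition in Table 5 is redacted. Either may hold the assignment rule. Neither is counted against the plan. They would not change the visible Table 4 entry, but they limit confidence in the cohort effect.

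Fourth, a reader might infer that misplaced patients weigh more because "contractual obligations associated with these datasources require that they not be merged or combined". That does not follow. If a cohort with k misplaced patients among n is split evenly over m databases, the expected share in each is (k/m)/(n/m) = k/n, as before.

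Finally, the number of patients may be zero. That is correct and limits the importance of the point, but the entry is still inconsistent.

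**Conclusion.** The point holds as an inconsistency with a conditional consequence. The Table 4 class for bevacizumab conflicts with its own mechanism entry and with Section 4; confidence in that is high. Whether any cohort would be affected depends on the class column being used for assignment, which the visible text neither states nor excludes; confidence there is lower.

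The size is 14 of 16 bevacizumab regimen definitions with two possible cohorts, and an unknown number of patients. The study is descriptive, so no error rate, power or sample size is touched. Severity is minor.

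Item d in Section 6.1 would, read literally, also absorb IO monotherapy and the TKI monotherapies not named in item b. That is a separate, minor wording point and adds no weight to this one.

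**What to change.** Change the Table 4 class of bevacizumab from IO to VEGF antibody, the term Section 4 already uses. Bevacizumab alone or with a TKI then fits none of the IO or TKI cohorts and falls in Other, which agrees with the Section 6.1 list.

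Add one sentence saying how bevacizumab plus a checkpoint inhibitor is assigned. The documents do not settle this. A default of Other would move patients who did receive a checkpoint inhibitor out of the IO cohorts, so the choice is the sponsor's. Whatever is chosen, report the combination as an identified row, so that it is not pooled unseen with dual-checkpoint patients. The sentence belongs in the protocol, because Section 6.7 says that no separate SAP is required.

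The cost is one table cell, one sentence and one reporting row. IO cohorts may lose a few patients, number unknown. As separate tidying, Section 6.1 could say that its items a to c are focus regimens within the five Section 5 cohorts, with item d reworded to match.
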